**Table 1. Study milestones**

Milestone	Planned/completed date
Finalization of study protocol (version 1) and submission to the Institutional Review Board (IRB)	October 2019 (complete)
Initial structured data collection	November 2019 (complete)
Updated structured data collection	July 2020 (complete)
Start of chart review	August 2020 (complete)
End of chart review	December 2020 (complete)
Primary and secondary descriptive analyses	September 2021
CCI [REDACTED]	[REDACTED]
Unadjusted outcomes analyses	December 2021
Adjusted outcomes analyses	January 2022
Final study report	February 2022

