## 8.2. Setting

The study population will consist of patients with a diagnosis of hormone receptor-positive/human epidermal growth factor receptor 2-negative mBC who initiated a who initiated PB+FUL and CCI

The USON includes 1,200 affiliated physicians operating in over 470 sites of care across states and treats approximately 1 million US cancer patients annually.

**Figure 1** presents a graphical depiction of the study time periods, which are as follows:

- Study observation period: 01 February 2016 – 30 June 2020.\*
- Study identification period: 01 February 2016 – 31 December 2019.
- Index date: The date of initiation with PB+FUL or CCI during the study identification period. For PB+FUL, the date of the first administration of either drug will be used.
- Baseline: Assessment will be done for the data collected at the closest date prior to index within 30 days of index (in absolute value). Variables to be assessed at baseline are specified in **Table 2**.
- Prior medical history: Patients' available history in the iKnowMed (iKM) EHR will vary based on the length of disease and the time within the USON. The prior medical history period will end the day prior to the index date. Variables to be assessed with prior medical history are specified in **Table 2**.
- Follow-up: Patients will be followed through the end of the study observation period, date of last visit or date of death, whichever occurs first. For analysis, patients will have a potential of at least 6 months of follow-up duration; however, patients will have variable follow-up time periods, depending on their index dates and last contact dates.

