Reason for treatment discontinuation	Chart review	Treatment characteristics	Study observation period	
Data for discontinuation reason will exclusively come from chart review. Reviewers will be asked to select reason(s) as explicitly documented in patients' charts. If available, reason patients discontinued treatment will be abstracted:
 
 
Progression
 
Toxicity
 
Decline in performance status
 
Financial/insurance
 
Completed planned treatment
 
Death
 
Hospice
 
Patient preference (if other categories do not apply)
 

PFIZER CONFIDENTIAL

				Physician preference (if other categories do not apply) Other
Proportion of patients who advance/do not advance	iKM structured data + chart review (derived)	Treatment characteristics	Study observation period	The proportion of patients who advance and do not advance from the index treatment will be summarized as the count and percentage of the following: Patients with ongoing index treatment Patients who died following index treatment Patients who advanced to a subsequent treatment Patients who did not advance to a subsequent treatment for unknown reasons
Post-index treatment regimen	iKM structured data + chart review	Treatment characteristics	Study observation period	The regimen received by patients following discontinuation from the index treatment.
Time to chemotherapy	iKM structured data +chart review (derived)	Clinical outcomes	Study observation period	Time to chemotherapy will be defined as the interval (in weeks) between index treatment and start of chemotherapy as documented in the iKM EHR database. Patients with ongoing treatment at the study observation period will be censored on the study end date or the last visit date available in the dataset, whichever occurred first. rwDOT will be analyzed using the Kaplan-Meier method with 95% CIs, and summary tables of the number of events and censored patients at 6, 12, 18, 24, 30, and 36 months.

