Date of provider-documented progression or recurrent disease	Chart review	Clinical outcomes	Study observation period	The date of provider-documented progression or recurrent disease as explicitly noted by a clinician in a scan report or progress note. Frequently, this will be the date the provider recorded evidence of progression, not

PFIZER CONFIDENTIAL

				necessarily the date the radiologic assessment was made.
Real-world complete, improved or stable disease rate (clinical benefit rate)	Chart review (derived)	Clinical outcomes	Study observation period	In real-world research, the parameters underlying response as defined by RECIST criteria are often unavailable. As such, this study will assess response to treatment as documented by providers and capture real-world assessments of response, including complete response, improved disease and stable disease. This measure will be similar to clinical benefit rate as defined by RECIST criteria.
Clinical outcomes				
Last USON visit date	iKM structured data + chart review	Clinical outcomes	Study observation period	Each patient's most recent visit date, prior to or on close of study observation period will be recorded. A visit is defined as a physician encounter with the practice where either treatment is given or vital signs are recorded. For patients with a death date, this last visit date should occur prior to the death date. This will not be reported separately; it will be used in calculating the patient's available follow-up time as a descriptive measure. available follow-up time = Integer (latest of last visit date or death date – index date +1)
Death date	iKM structured data, chart review + external sources	Clinical outcomes	Study observation period	Date of death will be captured from the iKM EHR, limited access death master file (LADMF), national death index (NDI) and, possibly, other commercial sources of death information (the study team is confirming the utility of these sources). If dates conflict among the sources, the NDI, followed by the LADMF date will be prioritized. If severe data discordance is observed (i.e., death is reported to occur prior to the index date), then the iKM death date will be used. Further information on the sources of death information is presented in Section 8.4 .

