Follow-up duration	iKM structured data, chart review + external sources (derived)	Clinical outcomes	Study observation period	The duration between index and last follow-up date. Findings will be summarized as the mean ( $\pm$ SD) and median (range) for all patients within the specified cohort. The number of patients with available data will be reported.
Vital status	iKM structured data, chart review + external sources (derived)	Clinical outcomes	Study observation period	Patients without a date of death recorded in iKM, LADMF, NDI or other commercial sources of death information used for the study will be assumed to be alive at the end of the study. Those with a date of death in available records will be flagged as deceased. Further information on the sources of death information is presented in Section 8.4 .
Overall survival (OS)	iKM structured data, chart	Clinical outcomes	Study observation period	OS will be defined as the interval (in weeks) between index treatment and the date of death (any cause) as documented in the iKM EHR database, LADMF, NDI and other

	review + external sources (derived)			commercial sources of death records that may be used for this study. Patients who did not die within the study observation period will be censored on the study end date or the last visit date available in the dataset, whichever occurred first. OS will be analyzed using the Kaplan-Meier method with 95% CIs, and summary tables of the number of events and censored patients 6, 12, 18, 24, 30, and 36 months.
Survival rate	iKM structured data, chart review + external sources (derived)	Clinical outcomes	Study observation period	Survival rates will be provided along with the Kaplan-Meier OS analyses described above as survival rates at 6, 12, 18, 24, 30, and 36 months.
Real-world progression-free survival (rwPFS)	iKM structured data, chart review + external sources (derived)	Clinical outcomes	Study observation period	The rwPFS will be measured from the initiation of the index treatment to the date of progression or date of death due to any cause, censoring patients who are still alive at the end of the study observation period and did not progress at the last visit date. The rwPFS will be estimated in weeks using the Kaplan-Meier method with 95% CIs, and summary tables of the number of events and censored patients at 6, 12, 18, 24, 30, and 36 months.

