Death information is updated weekly in the LADMF and is as current as it is reported to the Social Security Administration. However, death dates recorded in the LADMF are not complete due to limitations on access of records for research purposes. Levin et al. (2019) compared LADMF and hospital death records after access restrictions imposed in 2011. After 2011, LADMF sensitivity for in-hospital deaths was 14.8% (compared with 88.9% before 2011) and 28.9% for out-of-hospital deaths (compared with 71.4% before 2011). The LADMF specificity, however, was greater than 99% both prior to and after 2011. Peters et al. (2017) compared capture of death dates in the LADMF with a multiphase approach that assessed online databases (including LADMF), EHR records and provider follow-up. The authors reported that 42.7% of death records were identified by the LADMF, with the remainder from another online database (32.6%), EHR records (22.2%) and provider follow-up (3.5%). Overall, the sensitivity was 58.5%, with 100% specificity.

In a study of the iKM EHR database and LADMF, it was observed that 93.3% of all death records were captured in structured fields and 6.7% of death records were solely identified by the LADMF. Among deaths recorded by both structured data and the LADMF, concordance was 88.0%. When both structured and unstructured data are available, 99.4% of death records are captured from these sources, with 0.6% death records solely identified by

the LADMF. Between 2015 and 2019, the proportion of death records captured by structured data trended upward (slope = 4.04).

Death records in the NDI index are updated quarterly with a lag time of approximately 1 year. Curtis et al. (2018) compared several sources of death, including EHR data, Social Security Death Index and commercial death data, with the NDI, for a cohort of patients with non-small cell lung cancer. The sensitivity between the NDI and structured data was 66% and the specificity was 97%. With combined EHR and commercial death dataset, sensitivity increased to 84%. Inclusion of the Social Security Death Index increased sensitivity to 89% and, last, with supplementation of missing death information through chart abstraction (unstructured data), sensitivity increased to 91%. No studies to date have compared the capture of death information with the iKM EHR to the NDI.

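### Overall survival counts deaths after the last visit but censors everyone else at the last visit, and the death-date and follow-up rules conflict

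*Protocol*

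**What the plan says.** **Censoring.** Protocol Section 8.3, Table 2 (OS row), SAP Section 5.1 and SAP Table 1 share one rule: "Patients who did not die within the study observation period will be censored on the study end date or the last visit date", whichever is earlier. Table 2 defines the last visit as follows: "Each patient's most recent visit date, prior to or on close of study observation period will be recorded".

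**Deaths.** Table 2 takes deaths from the iKM record, the Limited Access Death Master File (LADMF), the National Death Index (NDI) and possibly commercial sources. It expects deaths after the last visit: "For patients with a death date, this last visit date should occur prior to the death date". The vital status row assumes that patients with no death record are alive at study end.

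**End of follow-up.** The Table 2 formula runs to the "latest of last visit date or death date". Protocol Section 8.2 and SAP Section 2.1.1 say instead: "Patients will be followed through the end of the study observation period, date of last visit or date of death, whichever occurs first".

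**Linkage timing.** Section 8.4 says: "Death records in the NDI index are updated quarterly with a lag time of approximately 1 year". Protocol Table 1 puts the milestone "Unadjusted outcomes analyses" in December 2021 and the adjusted analyses in January 2022. No visible text gives a date through which death linkage is complete.

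**Death-date priority.** Table 2 and SAP Table 1 rank NDI above LADMF. Protocol Section 8.4 and SAP Section 2.1.2 rank LADMF above NDI.

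**The concern.** Kaplan-Meier estimation needs censoring that does not depend on whether the patient later dies. Here two patients with the same index date and the same last visit are treated differently because of what happens afterwards. The one found dead contributes time up to death; the one who stays alive loses all time after the visit. Survivors are removed from the risk set early while the deaths stay in, so the estimated hazard is too high.

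OS and the survival rates at 6 to 36 months are planned results. Without a departure rate, a capture rate or a linkage-complete date, a reader could not tell how far, or in which direction, they are off. The conflicting death-date rules add a separate problem: two programmers could follow the text and derive different OS times for the same patient.

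**Working it through.** There is no OS, event-count or power figure in the visible text to reproduce.

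**1. The censoring rule.** Let V be the last visit and E the study end, 30 June 2020. By definition V ≤ E, so min(E, V) = V for every patient without a death, and the study-end branch never applies. A death at D ≤ E counts at D, even when D is later than V. Time between V and E therefore enters only for patients found dead.

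**2. Size with every death captured.** From the documents: index dates 1 February 2016 to 31 December 2019 and E = 30 June 2020, giving about 6 to 53 months of potential follow-up. Assumed: uniform index dates, exponential OS, exponential departure at 5/10/20% per year, and a hazard after departure of 1, 2 or 4 times the original. The simulation used 600,000 patients per scenario; repeat runs agree to within about 0.2 points.

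At a 40-month median with unchanged hazard, true 36-month OS is 0.5^(36/40) = 53.6%. A 108-month median follows from the 79.4% three-year OS cited in protocol Section 6 for treatment-naive patients: 36 × ln 2 / (−ln 0.794) = 108.

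| Median | Hazard after leaving | 36-month error of planned rule, points, at 5/10/20% leaving |
|---|---|---|
| 40 | ×1 | −2.0 / −4.3 / −9.1 |
| 40 | ×2 | −1.4 / −3.0 / −6.7 |
| 40 | ×4 | −0.6 / −1.4 / −3.3 |
| 108 | ×1 | −1.3 / −2.8 / −6.6 |

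Censoring at 30 June 2020 gives an error of about 0 in all of these. With nobody leaving, the gap between visits alone costs about −0.5 (monthly visits) to −1.5 (quarterly). For scale, the standard deviation of the 36-month estimate is about 3.5 points at n = 317, the first-line count in protocol Table 3.

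**3. When leavers' deaths are missed** (median 40, 36 months, points):

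| Capture of leavers' deaths | Leaving per year | Hazard | Planned rule | Study-end censoring |
|---|---|---|---|---|
| 70% | 10% | ×1 / ×2 / ×4 | −3.2 / −1.1 / +1.1 | +1.7 / +2.9 / +4.3 |
| 91% | 5 / 10 / 20% | ×4 | −0.2 / −0.8 / −2.1 | +0.7 / +1.3 / +2.4 |

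Study-end censoring has the smaller error only when capture is at least about 55–65% (×1), 80–85% (×2) or 95% (×4).

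**4. Linkage timing.** With a lag of about 1 year, an NDI search at the July 2020 data pull is complete to about July 2019. A search at the end of chart review (December 2020) reaches about December 2019. A search in December 2021 reaches about December 2020. Coverage to 30 June 2020 was therefore feasible from about mid-2021, before the outcomes analyses.

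**5. The conflicts side by side.**

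| Item | Protocol Table 2, SAP Table 1 | Elsewhere |
|---|---|---|
| Priority | NDI, then LADMF | LADMF, then NDI (protocol 8.4, SAP 2.1.2) |
| Override trigger | Death recorded before index | Visit after the recorded death, or sources more than 6 months apart (same sections) |
| Date used after override | iKM date | Not clearly stated (same sections) |
| End of follow-up | Later of last visit and death | Earliest of study end, last visit and death (protocol 8.2, SAP 2.1.1) |
| Sources for OS | Commercial sources allowed | Commercial sources not listed (SAP 5.1) |

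**The case against.** **The bias may be small.** Leavers are plausibly sicker: hospice and "Decline in performance status" are listed reasons for stopping treatment. At four times the hazard and a 40-month median, the 36-month error stays below one standard deviation even at 20% leaving per year. This stands as a limit on size. It does not make the rule symmetric.

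**Study-end censoring is not always better.** This stands. It overstates OS when deaths are missed, and at 91% capture with ×4 hazard its error is slightly larger than that of the planned rule. A linkage date of 30 June 2020 alone is therefore not enough; the search must also find the deaths.

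**Capture may already be good.** Section 8.4 reports that 99.4% of death records were found in structured plus unstructured iKM data. That compares iKM with LADMF only, and the same section says iKM capture has not been compared with NDI. It is useful context, not a sensitivity estimate.

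**The linkage date may exist.** One row of the milestone table is redacted, so the point is limited to visible text.

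**Stronger readings.** A reader might infer that the Section 8.2 follow-up wording removes deaths from OS altogether. It does not: it is a general statement, and the OS row specifically counts deaths. The wording needs aligning, nothing more. A reader might also infer that OS is certain to be understated. That holds only with sufficiently complete capture; the sign can reverse. The omission of commercial sources from SAP Section 5.1 is minor, since their use is conditional throughout.

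**Conclusion.** The concern holds. Both documents censor survivors at the last visit while counting later deaths, so censoring depends on the outcome. This part and the conflicts in death-date priority, override and follow-up wording follow from the text without assumptions.

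The size is conditional. With full capture, the scenarios tabulated give a 36-month error from −0.6 to −9.1 points, smaller at earlier time points. These figures rest on exponential survival and assumed departure rates and hazards, none of which the documents supply. The priority conflict has no fixed direction and affects only deaths whose sources disagree.

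OS is a descriptive secondary endpoint and no primary objective is affected. It should be corrected before the OS results are produced.

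**What to change.** 1. Run the NDI and LADMF search late enough to cover deaths to 30 June 2020, and state the linkage-complete date.
   - If linkage is complete to that date and NDI is searched for all patients, censor patients without a death at 30 June 2020 as the main OS analysis and report the planned last-visit rule beside it. Give the number last seen more than 90 days before cut-off and the number of deaths found only through external sources. When some deaths are missed, study-end censoring overstates OS while the planned rule usually understates it, so the pair is informative. It is not a guaranteed bracket: at 70% capture and ×4 hazard both overstate.
   - If linkage or capture falls short, keep the planned rule, report study-end censoring as the sensitivity analysis, and state the likely direction of each.
   - An analysis with the same window after the last visit for deaths and survivors is optional. Label it as overstating OS when leavers are sicker: with a 3-month window, about +3.1/+6.0/+10.9 points at 36 months for ×4 and 5/10/20% leaving.
2. Use one NDI/LADMF order, one set of overrides with a stated resulting date, and one source list in protocol Table 2 and Section 8.4 and in SAP Table 1 and Sections 2.1.2 and 5.1.
3. Reword the follow-up definition in protocol Section 8.2 and SAP Section 2.1.1 to agree with the Table 2 formula and the OS row.
4. Check whether the same asymmetry affects the death component of rwPFS.

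Cost: wording in both documents and one extra run, plus an NDI refresh if the existing search falls short.

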#### 8.4. Data sources

**Table 2** presents the data elements that will be evaluated through this study and their associated source. Most study data will originate from the EHR system of the USON, iKM. iKM captures outpatient practice encounter histories for patients under community-based care, including, but not limited to patient demographics such as age and gender; clinical information such as disease diagnosis, diagnosis stages, performance status information and

laboratory testing results; and treatment information, such as dosages and treatment administration within the USON.

Structured data fields within the iKM EHR database will provide information needed to address most research questions. These data will be supplemented by additional unstructured data collected through chart review for a subset of the study population (selection methodology described in **Section 8.2.4**). Electronic chart review data was collected by means of a secure, web-based electronic case report form (eCRF) by healthcare professionals with oncology experience.

The study will only use data from USON practices utilizing full EHR capacities of iKM. Data management and administrative processing is supported by McKesson's quality assurance procedures. Additionally, iKM has previously been used to evaluate patient profiles, treatment patterns and outcomes among mBC patients and the results have been consistent with other published studies. Thus the study team does not plan to conduct any additional studies to validate the accuracy of demographic, clinical, treatment and outcome information in the iKM EHR database.

The primary source of death information will be structured and unstructured records of death in the iKM EHR database. McKesson has certification to access the LADMF of the Social Security Administration and, as such, this will be a supplementary source of vital (death) records in addition to the NDI of the Centers for Disease Control. The study team is also evaluating the potential for other commercial sources of death information to be used for this study, including ObituaryData.com, Legacy.com, Datavant and others. If it is confirmed that these sources can be used, they will be an additional source of death information.

Death information is updated weekly in the LADMF and is as current as it is reported to the Social Security Administration. However, death dates recorded in the LADMF are not complete due to limitations on access of records for research purposes. Levin et al. (2019) compared LADMF and hospital death records after access restrictions imposed in 2011. After 2011, LADMF sensitivity for in-hospital deaths was 14.8% (compared with 88.9% before 2011) and 28.9% for out-of-hospital deaths (compared with 71.4% before 2011). The LADMF specificity, however, was greater than 99% both prior to and after 2011. Peters et al. (2017) compared capture of death dates in the LADMF with a multiphase approach that assessed online databases (including LADMF), EHR records and provider follow-up. The authors reported that 42.7% of death records were identified by the LADMF, with the remainder from another online database (32.6%), EHR records (22.2%) and provider follow-up (3.5%). Overall, the sensitivity was 58.5%, with 100% specificity.

In a study of the iKM EHR database and LADMF, it was observed that 93.3% of all death records were captured in structured fields and 6.7% of death records were solely identified by the LADMF. Among deaths recorded by both structured data and the LADMF, concordance was 88.0%. When both structured and unstructured data are available, 99.4% of death records are captured from these sources, with 0.6% death records solely identified by

the LADMF. Between 2015 and 2019, the proportion of death records captured by structured data trended upward (slope = 4.04).

Death records in the NDI index are updated quarterly with a lag time of approximately 1 year. Curtis et al. (2018) compared several sources of death, including EHR data, Social Security Death Index and commercial death data, with the NDI, for a cohort of patients with non-small cell lung cancer. The sensitivity between the NDI and structured data was 66% and the specificity was 97%. With combined EHR and commercial death dataset, sensitivity increased to 84%. Inclusion of the Social Security Death Index increased sensitivity to 89% and, last, with supplementation of missing death information through chart abstraction (unstructured data), sensitivity increased to 91%. No studies to date have compared the capture of death information with the iKM EHR to the NDI.

Some data elements will be available from multiple sources, structured data (i.e. from iKM), unstructured data (i.e. chart review), the LADMF, NDI and, possibly, commercial sources of death records. During chart review, abstractors reviewed patients' entire medical record, including information that is also captured in structured fields. Discrepancies in the medical record will be reviewed by McKesson's Data Quality Manager, Medical Director/Physician Investigator to determine the most appropriate value to be abstracted based on clinical judgement and operational guidelines.

If there is a discrepancy in dates of death among the sources, the LADMF date, followed by the NDI date will be prioritized as it reflects the official date of death reported to government agencies unless: 1) EHR activity indicates that a patient visit occurred after date of death as documented in the LADMF or NDI; 2) date of deaths between the two sources vary by more than 6 months. In these cases, the date of death recorded in the iKM EHR as part of patient follow-up by USON physicians and staff may be sourced from non-official records, including telephone conversations with the patient's family.

Data from all sources and any derived variables will be merged into one master dataset for analysis. Data will be handled in compliance with the Health Insurance Portability and Accountability Act (HIPAA) and Health Information Technology for Economic and Clinical Health (HITECH).

